Aim 1. Maximize exercise-mediated recovery of limb muscles by using stimulation induced spinal plasticity. We will study the effect of limb training combined with Spike-Timing Dependent Plasticity (STDP) on motor function recovery. We will test the effect of three groups: (1) stimulation, (2) training +stimulation, and (3) training+sham stimulation. We hypothesize that the ability of training to promote recovery of limb motor function will be enhanced by eliciting STDP in upper and lower-limb. An important strength of this aim is the combination of training and STDP, which aims at enhancing the beneficial effects of motor training by promoting plasticity in the corticospinal pathway (Ellaway et al., 2007; Castel et al., 2009). Training effects on physiological pathways will be explored and correlated with hand/arm motor function and the site and extent of the lesion defined by structural MRI.

Aim 2. Maximize exercise-mediated recovery of limb muscles by using stimulation induced spinal plasticity. STDP has been shown to be effective in enhancing the recovery of residual limb function in humans with chronic incomplete SCI (Urbin et al., 2017). In this aim we will investigate the effect of the combination of extended STDP and training. We hypothesize the ability of training to promote recovery of motor function will be enhanced by eliciting STDP in the corticospinal pathway.

BACKGROUND:

After a SCI, many individuals present deficits in upper-limb and/or lower-limb function. Most SCIs are contusions and ~50% occur at the cervical level causing anatomically incomplete damage and bilaterally functional deficits to lower- and upper-limbs (Kakulas, 1999). Arm and leg function deficits limit daily-life activities, such as reaching and grasping, eating, writing, and walking which decreases the quality of life (Snoek et al., 2004). Regaining arm and leg function is considered the highest priority for improving the quality of life of individuals with SCI (Anderson, 2004).

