If eligible, participants will be asked to complete pre, post, and follow-up assessment sessions in addition to the training sessions. Each assessment will require 2-5 sessions. Participants will complete up to 135 training sessions with a maximum of 360 paired pulses of stimulation and a small cohort of participants (n=10) will complete up to 270 training sessions with a maximum of 720 paired pulse of stimulation (up to 4 times per day). This will be determined based on preliminary data. In Aim 1, participants will be tested before and after at least 10 training sessions with single site stimulation. In Aim 2, participants will be tested before and after at least 40 training sessions with multisite stimulation. If a training session is not completed or missed participants will be asked to recover that session in a timely manner.

AIM 1: Randomized controlled design

Pre-assessment: 1. Physiology 2. Kinematics 3. Function	Stimulation Training + stimulation Training + sham stimulation	Post-assessment: 1. Physiology 2. Kinematics 3. Function	Follow-up assessment: 1. Physiology 2. Kinematics 3. Function
--	--	---	--

AIM 2:

Pre-assessment: 1. Physiology 2. Kinematics 3. Function	Training + stimulation	Post-assessment: 1. Physiology 2. Kinematics 3. Function	Follow-up assessment: 1. Physiology 2. Kinematics 3. Function
--	------------------------	---	--

We anticipate that each participant will take about 2-10 months to complete the study procedures/testing. Follow-up assessments will be done 1-9 months after completion of protocol, one follow-up in the first 3 months and the last follow-up in the 4-9 months following the last completed session. We will evaluate the subject's ability to move their hands, arms, legs, feet and/or toes using the different physiological and functional tests as mentioned above. TMS measurements, CMEPS and EMG recordings may also be done at these follow-up assessments.

INCLUSION AND EXCLUSION CRITERIA:

We anticipate the screening of 500 subjects across the two aims (60 subjects for Aim 1, and 40 for Aim 2) who have incomplete SCI at the cervical/thoracic/lumbar level (C2-L2). This number accounts for an attrition rate of 50%. To account for screen failures we would like to ask for a total of 200 subjects.

- Inclusion criteria for SCI subjects:
 - (1) Male and females between ages 18-85 years
 - (2) SCI at least 4 weeks post injury
 - (3) Spinal Cord injury at or above L2
 - (4) ASIA A,B,C, or D, complete or incomplete

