 - (5) Possess the following abilities
 - (Aim 1) The ability to produce a visible precision grip force with one hand, and/or the ability to perform some small wrist flexion and extension (Aim 2) The ability to perform a small visible contraction with dorsiflexion and hip flexor muscles

- Exclusion criteria for SCI Subjects:
 - (1) Uncontrolled medical problems including pulmonary, cardiovascular or orthopedic disease
 - (2) Any debilitating disease prior to the SCI that caused exercise intolerance
 - (3) Premorbid, ongoing major depression or psychosis, altered cognitive status
 - (4) History of head injury or stroke
 - (5) Vascular, traumatic, tumoral, infectious, or metabolic lesion of the brain, even without history of seizure, and without anticonvulsant medication
 - (6) History of seizures or epilepsy
 - (7) Receiving drugs acting primarily on the central nervous system, which lower the seizure threshold (see appendix 2)
 - (8) Pregnant females
 - (9) Ongoing cord compression or a syrinx in the spinal cord or who suffer from a spinal cord disease such as spinal stenosis, spina bifida, MS, or herniated disk
 - (10) Metal plate in skull
 - (11) Individuals with scalp shrapnel, cochlear implants, or aneurysm clips

RECRUITMENT METHODS:

We anticipate screening of 500 subjects to complete the study (see description above). We will be using the IRB approved SCI registry for recruitment. A letter granting access to the registry is included in the submission. Subjects who have previously expressed an interest in participating in research studies at the Shirley Ryan AbilityLab complete a questionnaire and request that their information be entered into the research volunteer database. This database is searchable based on criteria such as age, time-post injury and injury level. Potential subjects will be called by the study coordinator. If the individuals have not agreed to be contacted by phone for future studies then the treating physician will be the one contacting them. The phone call will be to provide information about the study to the individual to determine if they are interested in the study. We will not be collecting any information from the individual. All the screening will be done after written consent is collected and before enrollment.

COMPENSATION FOR PARTICIPATION IN RESEARCH ACTIVITIES:

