Please be advised: Inactivity on the card for more than 3 months will incur a monthly fee. However, as long as there is activity on the card within 3 months (funds are added or a transaction is completed), the month period will reset and no monthly fee will be assessed. If the participant do incur a monthly fee, please contact Greenphire Support at the number on the back of the card and they will reverse the fee. See "Tips for Using the Attached ClinCard" for more information. The Finance Department at the Rehabilitation Institute of Chicago will be provided with the participant's information, including their Social Security Number, in order to issue payment for the study participation. Study payments are considered taxable income and reportable to the Internal Revenue Service (IRS). An IRS Form 1099 will be sent to the participant if the total payments are \$600 or more in a calendar year.

The participant may be given access to new inventions that are being developed by the investigator, the study sponsor, or other people involved in the study. Certain laws can make it harder to obtain legal protection for a new invention shared with a study participant, unless the study participant agrees to keep information about the invention confidential. The participant agree to keep confidential information they may receive about new inventions, such as new drugs, new devices, or new methods.

WITHDRAWAL OF PARTICIPANTS:

Subjects will be allowed to withdraw from the study at any time upon request. Their participation will be terminated if any of the inclusion criteria ceases to be valid or if any exclusion criteria will manifest after enrollment. Occurrence or participant reporting of any of the following during the course of the study may lead to withdrawal by study team:

- Change in dosage for neuro-active medications (Baclofen, Lyrica, Celebrex, Cymbalta, Gabapentin, Naprosyn, Diclofenac, Diazepam, Tramadol, etc.) within 2 weeks of any study visit.
- Skull fractures, skull deficits or concussion within the last 6 months
- Unexplained recurring headaches
- Sleep deprivation, alcoholism
- Claustrophobia precluding MRI
- Pregnancy

RISKS TO PARTICIPANTS:

Muscle Activity Recording (EMG): Mild discomfort, such as tingling, an itching sensation may be felt under the electrodes that register the response in the participants muscles. We will clean the area with alcohol and use standard, hospital grade electrodes.

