Peripheral Nerve Stimulation/Spinal stimulation/MEPs/CMEPs/H-Reflex: Intensity will be increased gradually during the electrical stimulation evaluations when necessary. Mild discomfort, such as an itching sensation may be felt under the electrode that stimulates the targeted nerve(s) or under the electrodes that register the response in the muscle(s). We will clean the area with alcohol and use standard, hospital grade electrodes. Another risk of the nerve stimulation used in this research is that participants might feel mild pain, if pain fibers could be activated. Skin irritation due to the use of self-adhesive surface electrodes is possible but will be minimized by cleaning the skin with alcohol before and after the application of the electrodes.

MRI scan: Subjects, investigators, and facility staff will be examined by a hand-held screening device for magnetic material before entry and each re-entry to the scan room. Warning signs, including the specific dangers of high magnetic fields, are posted in the necessary location. The standard 3 Tesla Magnet will be used for testing. The MRI exam involves no exposure to x-rays or radioactivity, and is safe. The FDA approved the Siemens 3-T scanner, which time varying magnetic fields (gradient), specific absorption rate and acoustic noise levels. FDA guidelines will be strictly enforced at our 3T scanner. Subject Screening: The magnetic field will affect any metallic object. In order to avoid risks associated to heating or motion of metallic parts in the body, all individuals will be carefully screened and will have to complete a safety check form (separate file uploaded in the documents list). Potential Risks: Some individuals feel uncomfortable in enclosed spaces, as in the MRI (claustrophobia). The individual can stop the test at any time by squeezing an emergency stop squeeze ball he/she will hold in their unimpaired hand.

JTT/9HPT/CAHAI/GRASSP/EPT/TRI-HFT: Individuals will have resting periods as needed, all procedures will be explained in detail and subjects will be informed that they can stop the experiment at any time.

Portable Spasticity Assessment Device (PSAD): Mild discomfort, such as tingling, an itching sensation may be felt under the electrodes that register the response in the participants muscles. We

will clean the area with alcohol and use standard, hospital grade electrodes. Possible skin irritation from the attachment of arms straps.

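### The only stated way to stop an MRI in progress needs an unimpaired hand, which some eligible Aim 1 participants will not have

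*Combined protocol and SAP*

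**What the plan says.** The MRI scan paragraph under Risks to Participants names claustrophobia as a potential risk and answers it with a squeeze ball: "The individual can stop the test at any time by squeezing an emergency stop squeeze ball he/she will hold in their unimpaired hand". It describes no other signal from inside the scanner.

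MRI enters the study through Aim 1 in the Objectives, where training effects on physiological pathways are to be "correlated with hand/arm motor function and the site and extent of the lesion defined by structural MRI".

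The Background describes cervical injuries as "causing anatomically incomplete damage and bilaterally functional deficits to lower- and upper-limbs". The Inclusion and Exclusion Criteria admit injuries from C2 to L2 and all ASIA grades from A to D. The ability required for Aim 1 is: "The ability to produce a visible precision grip force with one hand, and/or the ability to perform some small wrist flexion and extension".

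The Withdrawal section lists "Claustrophobia precluding MRI" under the lead-in that "any of the following during the course of the study may lead to withdrawal by study team".

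**The concern.** The stop instruction assumes one-sided impairment, as if every participant had a good hand to fall back on. The protocol describes a population in which both arms are commonly affected, and Aim 1 deliberately recruits people with limited hand function. The protocol names the risk (distress in an enclosed space) and promises that the person can end the scan at any moment. If someone cannot work the ball, that promise fails, and the MRI text offers nothing in its place. What is at stake is participant safety and the truth of an assurance given to participants, not the validity of any estimate.

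**Working it through.** No figure is involved, so the check sets the relevant sections side by side.

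1. **Is MRI planned for people with impaired hands?** Yes. The Aim 1 objective uses structural MRI to define the lesion and relates it to hand and arm function.

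2. **Can an Aim 1 participant have two impaired hands?** Yes. Injury levels start at C2, the Background describes bilateral upper-limb deficits after cervical injury, and none of the 5 inclusion or 11 exclusion criteria asks for an unimpaired hand. The Kinematics entry under Study Endpoints speaks of the less affected arm in participants, which itself implies that the other arm is not the only one affected.

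3. **Does entry guarantee a usable grip?** No. The Aim 1 criterion joins its two abilities with and/or, so small wrist flexion and extension is enough. Entering that way does not prove that grip is absent, but it means that grip need not have been demonstrated.

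4. **Is there another way to stop a scan in progress?** None was found among the other stop, withdrawal and monitoring statements:
   - Withdrawal on request is general and gives no method of signalling from a scanner.
   - The entry on claustrophobia in the Withdrawal section is discretionary. It may remove some people beforehand, but claustrophobia is not an exclusion criterion and the entry does not act during a scan.
   - The stop statements for the hand-function tests and for TMS, and the invitation to interrupt for fatigue, do not address MRI.
   - Staff monitoring is stated for neuromechanical testing and the presence of a team member is stated for TMS. Neither is stated for MRI.
   - The MRI safety check form is introduced for metal screening. It is a separate file and was not available.
   - The physician authorization under Spinal stability covers all procedures, but it is sought for spine stability and provides no signal.

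5. **How many people are affected?** This cannot be derived. MRI is named only in the Aim 1 objective, the Withdrawal section and the MRI risk paragraph. It is not among the 19 listed measurements (A to S), and the Aim 1 schedule shows only "Pre-assessment: 1. Physiology 2. Kinematics 3. Function", with the same three domains at post-assessment and follow-up. The number scanned, the share entering on wrist movement alone and the force needed to trigger the ball are all missing, so no range is offered.

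**The case against.** The strongest reply is that only one ill-fitting word has been shown, not a harm. A sensible operator would read *unimpaired* as *better*, and many people with two impaired hands can still squeeze a ball. The Upper limb training section supports this in part. Its passive and active-assisted options are stated after gross grasping, fine grasping and hand cycling. The separate thumb-and-index task that follows asks for 5%, 20% or 30% of maximum voluntary contraction, a 3-second hold and 300 trials, with no passive option stated. Exposure is also unknown, the safety check form and the consent pages were not seen, and the claustrophobia and physician-authorization provisions narrow the group at risk.

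Much of this stands as a limit on size. Inability to squeeze is not demonstrated for anyone, and a document not supplied could contain a further signal. It does not remove the mismatch. The training task is an activity and not an entry criterion, and the criterion that governs entry does not require grip. Using the better hand still leaves the protocol with no check that this hand can trigger the ball and no fallback if it cannot. None of the partial safeguards, as described, works once the scan has begun.

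**Conclusion.** The concern holds. For Aim 1 participants with two impaired hands, the only stated means of stopping a scan in progress cannot be followed as written, and the eligibility criteria admit such people. The conclusion is limited to Aim 1 and to the text supplied; it assumes that the separate safety check form and the consent pages add no in-scan signal. It does not establish that any given participant would be unable to stop a scan, and the number affected cannot be estimated. Confidence is medium. The change is worth making because the protocol relies on this safeguard for a risk that it names itself, and because correcting it costs little.

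**What to change.** In the MRI scan paragraph, replace the reference to the unimpaired hand with wording such as:

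*The ball will be held in the less affected hand, after the participant has shown before the scan that he/she can trigger it. If this is not possible, an adapted trigger or continuous voice contact will be used. The scan will not proceed without a working stop signal.*

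The term *less affected* matches what the Kinematics entry already uses for the participant's arm.

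The cost is one changed sentence and a short check before each scan. The one drawback is that a scan may occasionally be missing from an exploratory correlation. GRASSP, the 10-meter walk test and their analysis are unaffected.

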Neuromechanical Testing: There is the potential to cause too much stretching, which may cause pain or damage to the joint. A number of safety features are implemented to attempt to reduce these risks, such as mechanical stops and limit switches. Research staff will monitor the subject while using this equipment.

TMS procedures: The TMS system stimulates the brain non-invasively. It generates a small magnetic field across the subject. TMS is widely used in clinical research, and the risks of TMS are believed to be very low. However, there is the very slight chance that TMS can cause a seizure. There is no ionizing radiation exposure involved and the studies are non-invasive. All participants will be screened before enrollment to assure that they meet study criteria and that there are no contraindications to TMS.

Subjects will be instructed that they can discontinue the TMS experiment at any time. In the unlikely event of a seizure, ROC stat will be contacted immediately. If a headache or mild scalp discomfort occurs, subjects will be directed to use over the counter pain medication at their own discretion. Earplugs will be available to minimize any type of hearing damage that might possibly occur due to the sound generated by the TMS equipment. An authorized study team member will be present during all TMS procedures.

Although very unlikely, it is theoretically possible that the participant may have a seizure induced by the TMS. Considering the large number of individuals who have undergone TMS studies since 1998 and the small number of seizures, we can assert that the risk of TMS to induce seizures is certainly very low (see review by Rossi et al., 2009). However, we will inform the participant about this unlikely risk. If a seizure occurs, it will occur during the TMS application itself, not after. When a seizure happens the participant's brain starts acting strangely and participants may feel dizzy and have repetitive rhythmic movements of any part of their body. If this unlikely event happens, we will immediately call ROC stat.

In the unlikely event of a seizure, a standard seizure protocol will be followed:

1. Cushion the head and area so subject does not injure themselves.
2. Turn the subject on their side to prevent aspiration
3. Monitor the duration of the seizure
4. If the seizure ends in less than 60 seconds, monitor and contact ROC stat.
5. If the seizure lasts more than 60 seconds, activate emergency ROC stat services.

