Aim 1: Repeated-measures ANOVA and Tukey post hoc analysis will determine effects of GROUP (stimulation, training+stimulation, and training+sham), TIME (before, immediately after, and follow-ups around 3 and 6 months post intervention) on physiological and behavioral outcomes. For alpha (type I error) of 0.05 and 1-beta (power) of 0.8, 45 SCI participants (15/group) will be included.

Aim 2: Repeated-measures ANOVA and Tukey post hoc analysis will determine effects training stimulation, TIME (before, immediately after, and follow-ups around 9 months post intervention) on physiological and behavioral outcomes. For alpha (type I error) of 0.05 and 1-beta (power) of 0.8, 11 SCI participants will be included.

Audio/Video Taping:

We plan to audio and video taping some parts of the experimental session, upon subject consent (optional in the consent form). Recordings will be only of the experimental activities described in the protocol. The subjects' identity will be hidden if subjects do not explicit consent to be recognized from the video or audio. The audio and video records will be stored in a password-protected file on a USB drive in a locked cabinet in the PI's office at the Rehabilitation Institute of Chicago.

The audio and video records will be used only for:

- a) Medical or scientific publications;
- b) Presentation at conferences;

The audio and video records will be destroyed after the time period chosen in the consent form.

This study does not involve any other risk to the subject, beyond some sense of effort and mild fatigue. Fatigue will be assessed based on the subjects' verbal report. They will be explicitly invited to interrupt the experiment if they experience fatigue. All studies will be carried out in the hospital environment where medical care is immediately available if needed.

POTENTIAL BENEFITS TO PARTICIPANTS:

Participation in the experiment may result in no direct improvement or, in the rare and unanticipated event, worsening of the subject's condition, including prolonged recovery time.

DATA MANAGEMENT AND CONFIDENTIALITY:

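### The numbered seizure steps leave out the immediate call to ROC stat that the text requires twice; followed literally, the call comes up to about 60 seconds later

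*Combined protocol and SAP*

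**What the plan says.** All but one of the relevant statements are in the combined protocol and SAP under RISKS TO PARTICIPANTS, in the part on TMS procedures.

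- First statement: "In the unlikely event of a seizure, ROC stat will be contacted immediately".
- Second statement, at the end of the paragraph that explains the seizure risk: "If this unlikely event happens, we will immediately call ROC stat".
- The sentence that introduces the list: "In the unlikely event of a seizure, a standard seizure protocol will be followed".
- Steps 1 and 2 protect the head and surroundings, and turn the subject to prevent aspiration.
- Step 3: "Monitor the duration of the seizure".
- Step 4: "If the seizure ends in less than 60 seconds, monitor and contact ROC stat".
- Step 5: "If the seizure lasts more than 60 seconds, activate emergency ROC stat services".

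On staffing, the same part says "An authorized study team member will be present during all TMS procedures". On the setting, the paragraph on risk that closes the Audio/Video Taping section says "All studies will be carried out in the hospital environment where medical care is immediately available if needed".

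**The concern.** The two sentences of running text make the call unconditional and immediate. The list presented as the procedure to follow makes it conditional on how long the seizure has lasted. A staff member who works through the list in order would protect, turn and time the subject, and would reach an instruction to call only when the seizure stopped or passed 60 seconds.

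A numbered list is the form of instruction most likely to be used in an emergency, although the protocol does not say which text staff keep to hand. It guarantees one team member at TMS procedures. If only one is there, that person has to cushion, turn, time and call, and the written order then decides when help is summoned. The early steps may also take time here. During stimulation the head is strapped to a headrest (STUDY INTERVENTION(S), TMS paragraph), and inpatients with cervical injuries are tested with neck support (RISKS TO PARTICIPANTS, paragraph on spinal stability).

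What is at stake is participant safety in a rare event. Endpoints, sample size and analysis are not affected.

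**Working it through.** There is no power or sample-size figure to reproduce. The check sets the two instructions side by side and works out when each puts the call.

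**Inputs**

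- Running text, stated twice: call at onset, so the time of the call is 0 s whatever the duration.
- Steps 1 to 3: no call.
- Step 4: contact if the seizure has ended in under 60 s. Whether this applies is known only at the moment the seizure ends, at D seconds.
- Step 5: activation if the seizure lasts more than 60 s. Whether this applies is known only once 60 s have passed.

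ROC stat is thus mentioned in 0 of the first 3 steps and in 2 of all 5, both times with a condition on duration.

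**Formula**

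For a seizure of D seconds:

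- time of call under the text = 0
- time of call under the list, read literally = min(D, 60)
- delay = min(D, 60) − 0 = min(D, 60)

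**Results**

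The durations below are assumed for illustration. The protocol gives only the 60-second threshold.

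| D (s), assumed | Call under text (s) | Call under list (s) | Delay (s) |
|---|---|---|---|
| 15 | 0 | 15 | 15 |
| 30 | 0 | 30 | 30 |
| 45 | 0 | 45 | 45 |
| 90 | 0 | 60 | 60 |
| 180 | 0 | 60 | 60 |

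The delay rises with the length of the seizure and levels off at about 60 s.

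Two details of the list qualify this:

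- Step 4 puts monitoring before contact and sets no time limit for it, so about 60 s is not a strict ceiling on that branch.
- A seizure of exactly 60 s falls under neither step 4 nor step 5.

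**Can the two instructions be reconciled?** One can suppose an immediate call first, with the list then choosing the level of response. The stronger verb in step 5 fits that. Step 4 does not: it tells staff to contact ROC stat after a short seizure, which would repeat a call already made. The combined sequence is not written anywhere in the protocol.

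**After the change.** With the call placed at onset, the time under the list becomes 0 s and the delay becomes 0 − 0 = 0 s for every D.

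**The case against.** The strongest reply is that the instruction is not missing from the protocol. The second statement of the immediate call comes directly before the sentence that introduces the list. Nothing in the list tells staff to wait or says that it replaces that statement. Read together, staff would call, protect the subject, time the seizure and escalate if needed, and step 4 would merely be redundant. On that view the delay exists only for someone who reads the list without the sentence above it.

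The harm argument also rests on inference. The documents do not say that staff work from this list, the protocol refers to a separate TMS safety checklist that is not available here, and one team member present is a minimum rather than a description of staffing. Nothing in the documents shows that a call made up to a minute later, with staff attending, changes the outcome. Finally, putting the call first could delay head protection and turning if only one person is there.

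Much of this stands. The combined reading is possible, the list does not forbid an earlier call, and no harm from the delay has been demonstrated. It does not remove the conflict. The list is introduced as what will be followed, it reads as a complete sequence, and its only calls depend on duration. If the combined reading is what was intended, it still needs to be written down. The point about a lone staff member is a good one, and it is why a physician should settle the order for that case.

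**Conclusion.** The concern holds. The text requires an unconditional immediate call and the numbered procedure does not contain it. Read literally, the list moves the call from 0 s to min(D, about 60 s), possibly somewhat later on the step 4 branch because monitoring there has no time limit.

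The size of the delay rests on staff following the list in order without adding the call from the text. That is an assumption about behaviour and the documents do not settle it. The mismatch in wording does not depend on it.

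The practical consequence is limited. It arises only if a seizure occurs, which the protocol considers very unlikely; participants are screened for TMS contraindications, a team member is present, hospital care is at hand, and both written branches end with ROC stat being called. It should be fixed because it is safety text that contradicts the protocol's own commitment.

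**What to change.** Reword the list as follows:

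1. Call ROC stat at once, while cushioning the head and clearing the area.
2. Turn the subject on the side.
3. Time the seizure.
4. If it ends in under 60 seconds, continue monitoring until ROC stat has responded.
5. If it reaches 60 seconds or more, activate the emergency ROC stat services.

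This makes 60 seconds a threshold for escalation only, removes the repeated contact in step 4, and covers a seizure of exactly 60 seconds. The responsible physician should confirm the wording and state the order of actions when only one staff member is present, including how the call is made without delaying head protection and positioning.

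The cost is a rewording of five lines and a short staff briefing. Randomisation, endpoints, sample size and analysis are untouched.
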